5. TREATMENT PLAN

We will conduct a randomized placebo-controlled trial in patients with higher-risk monoclonal gammopathy of undetermined significance (MGUS) and low-risk smoldering multiple myeloma (SMM). After informed consent is signed, total of 60 eligible and evaluable participants will be randomized 1:1 either to metformin or placebo. Stratification factors will be disease stage (MGUS vs. SMM) and heavy vs. light-chain status. The treatment period will be 6 months and primary outcome assessments as outlined below will occur at baseline and after 6 months of treatment or for those that discontinue medication, as close to the 6-month timepoint as possible. To explore participants' willingness to continue to take metformin after the 6-month treatment period and observe longer-term response, participants will be given the option to learn their treatment assignment after completing the primary study endpoints. Any participant randomized to the metformin group will be invited to continue to take metformin for an additional 6 months.

Treatment will be administered on an outpatient basis. Reported adverse events and potential risks are described in Section 7. Appropriate dose modifications are described in Section 6.

Participants will dose escalate in a stepwise fashion beginning with 500mg and increasing by 500mg until they reach 1500mg. The duration of this study and corresponding treatment period is 6 months.

No investigational or commercial agents or therapies other than those described below may be administered with the intent to treat the participant's premalignancy.

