12. STATISTICAL METHODS

12.1 Study Design/Endpoints Sample Size and Power

We powered the study to detect clinically meaningful changes in the primary endpoint of M-protein and levels.⁶⁷⁻⁶⁹ To facilitate precise baseline calculations, we ascertained M-protein level data from a representative clinical sample of MGUS and SMM patients at Dana-Farber. Accordingly, assuming a standard deviation of 0.99 g/dL, a type I error rate of 0.05, 60 participants will provide 80% statistical power to detect a between group difference of 0.73 g/dL, and 90% power to detect a between group difference of 0.84 g/dL which are considered clinically meaningful changes.⁶⁹⁻⁷¹ Specifically, a change of 0.73 g/dL indicates that we are

powered to detect > a 10% change in M-protein within the 6-month intervention period. Notably, a 10% change is consistent with the definition of “evolving M-protein” concentrations by Ravi et al and others⁶⁸ and evolving M-protein concentrations of this magnitude are associated with a shorter time to progressing than patients with non-evolving disease. It is also notable that although this trial should have a minimal drop-out rate or MM-defining events (and need to initiate standard MM treatment) during the 6-month intervention period.

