12.2 Statistical Analysis

The primary hypothesis being tested in this trial is that patients randomized to metformin will experience a significant reduction in M-protein levels compared to patients randomized to the placebo. This parameter has been selected as the primary endpoint because of its known clinical utility in predicting progression to overt MM in MGUS and SMM patients.⁶⁷⁻⁶⁹ Changes in this endpoint will be evaluated from baseline to follow-up in the two groups using a repeated measures mixed-effects model that accounts for the correlation between baseline and follow-up measures and is generally robust to missing data. The baseline value of the dependent variable (M-protein level) and disease subtype will be included as covariates in the regression models. Group-by-time interaction terms will be included as fixed-effects in the regression model. Model fit will be assessed using standard methods. Primary analysis of this endpoint will utilize stratified testing and intention-to-treat methods, using data from all participants randomized to an intervention group.⁷² Secondary/exploratory analyses will evaluate the influence of metformin on M-protein level in a per-protocol analysis.

A study project manager who is not involved in the statistical analysis will request information on treatment allocation from the DFCI Research Pharmacy. The Research Pharmacy is permitted to give the project manager information after the trial is closed to accrual and data collection on primary endpoints have been completed. However, all individuals performing the statistical analysis will remain blind to treatment group (metformin vs. placebo) for the primary outcome analysis.

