12.4 Stratification Factors

Randomization will be stratified by disease stage (MGUS vs. SMM) and heavy- vs light-chain status.

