12.7 Analysis of Secondary Endpoints

The secondary endpoint of this trial will be changes in a variety of biomarkers detailed in section 1.2. Changes in continuous variable outcomes will be evaluated from baseline to follow-up in the two groups using a repeated measures mixed-effects model that accounts for the correlation between baseline and follow-up measures and is generally robust to missing data. The baseline value of the dependent variable and disease subtype will be included as covariates in the regression models. Group-by-time interaction terms will be included as fixed-effects in the regression model. Model fit will be assessed using standard methods. All primary analyses will utilize stratified testing and intention-to-treat methods.⁷²

For changes in gene expression patterns, the precise methods are subject to change pending advancements in technology, but a general overview is provided below:

Paired-ended reads will be aligned against UCSC hg19 human annotation using Tophat 2.0.10; read counts for each gene will be determined using HTSeq 0.5.4. A subset of cells with more than 100,000 total reads across all genes will be selected for further analysis (70-80% of cells). To determine population average gene expression, the read counts observed in each cell will be normalized by the effective library size, determined by edgeR ‘calcNormFactors’ method. NMF-based consensus clustering will be used to cluster all single-cell RNA profiles. We will use coexpression networks-based gene prioritization tool GRAIL (<https://www.broadinstitute.org/mpg/grail/>) to select the most promising genes using gene expression signature as seeds. Cufflinks and Cuffdiff will be used to identify differentially expressed genes between the treatment arms.⁷³

Metabolite features will be analyzed as measures of peak areas, which are proportional to feature concentration and can be compared for any given metabolite. The metabolite variables will be standardized to a mean of 0 and standard deviation of 1.

For optional treatment extenders, this analysis is exploratory. We will assess the proportion of participants who are willing to take metformin for an additional 6 months. We will also evaluate response, duration of response, and depth of response according to modified IMWG criteria, or by mass spectrometry assessment.

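### The primary and secondary models name one undefined disease subtype covariate, so they are not shown to include both randomisation stratification factors

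*Combined protocol and SAP*

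**What the plan says.** Two places in the combined protocol and SAP give the stratification, and they agree. Section 5: "Stratification factors will be disease stage (MGUS vs. SMM) and heavy vs. light-chain status". Section 12.4: "Randomization will be stratified by disease stage (MGUS vs. SMM) and heavy- vs light-chain status".

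Two places give the model covariates. Section 12.2, for M-protein: "The baseline value of the dependent variable (M-protein level) and disease subtype will be included as covariates in the regression models". Section 12.7, for secondary endpoints: "The baseline value of the dependent variable and disease subtype will be included as covariates in the regression models". Both describe a repeated-measures mixed model with group-by-time terms.

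Stratification comes up again as a property of the test. Section 12.2: "Primary analysis of this endpoint will utilize stratified testing and intention-to-treat methods". Section 12.7: "All primary analyses will utilize stratified testing and intention-to-treat methods". Section 12.6 only refers back to 12.2.

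**The concern.** Two factors are used to randomise and one further term enters the model. That term, disease subtype, is defined nowhere and matches neither factor's name. It could mean stage, chain status or a combination of the two. Stratified testing does not settle the matter, because no strata, test statistic or link to the mixed model is given. In 12.7 the phrase is attached to primary analyses, so its bearing on secondary endpoints is also unclear.

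Stratified allocation takes between-stratum variation out of the treatment comparison. If a stratifier that predicts the outcome is missing from the model, that variation stays in the residual. The reported standard error is then larger than the true one, the confidence interval is too wide and some power is given away. The open wording also leaves the analyst to choose the covariates of the primary model in a 60-participant trial. Section 12.2 keeps the analysts blind to treatment group, which limits that freedom but does not replace a stated model.

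**Working it through.** **1. The plan's own power figure.** Section 12.1 states: "assuming a standard deviation of 0.99 g/dL, a type I error rate of 0.05, 60 participants will provide 80% statistical power". The target at that power is 0.73 g/dL, and the section claims 90% power at 0.84 g/dL. With 30 per arm, the standard error of the difference is 0.99 × √(2/30) = 0.2556 g/dL. The noncentrality is 0.73/0.2556 = 2.86 and 0.84/0.2556 = 3.29. A two-sided t test at 0.05 with 58 degrees of freedom then has power 80.2% and 89.8%, so the figures reproduce. One-sided testing would give 88.7% and 95.0%, which do not match. The calculation contains no covariates, so the covariate question does not affect it.

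**2. Cost of leaving out a stratifier, in general.** Let R² be the share of residual variance that the omitted factor still explains after the baseline value and the other factor. In large samples under stratified allocation:
- ratio of reported to true standard error = 1/√(1 − R²)
- true size of the nominal 0.05 test = 2[1 − Φ(1.96/√(1 − R²))]

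Power is at 0.73 g/dL, by normal approximation, with 0.99 g/dL as the SD before adjustment.

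| R² | Standard error too large by | True size | Power, omitted | Power, adjusted |
|---|---|---|---|---|
| 0 | 0% | 0.050 | 81.5% | 81.5% |
| 0.02 | 1.0% | 0.048 | 81.7% | 82.3% |
| 0.05 | 2.6% | 0.044 | 82.1% | 83.4% |
| 0.10 | 5.4% | 0.039 | 82.8% | 85.3% |
| 0.20 | 11.8% | 0.028 | 84.2% | 89.1% |

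Even with the factor omitted, power does not fall below its R² = 0 value. What is lost is a gain that adjustment would have brought. The documents give no R².

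**3. What R² might be.** Assumptions, none from the documents: chain status is the omitted factor, 20% of participants are light-chain (variance v = 0.2 × 0.8 = 0.16), the analysis is ANCOVA with stage included, within-stratum variance is 1 at each visit, ρ is the baseline to follow-up correlation, and d is the chain effect in SD. Let x be the extra residual variance as a fraction of the fully adjusted residual variance. The standard error ratio is √(1 + x).

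*Case A, chain status shifts follow-up only:* x = v d²/(1 − ρ²), with ρ = 0.6.
- d = 0.4: 0.0256/0.64 = 0.04, ratio 1.020
- d = 0.8: 0.1024/0.64 = 0.16, ratio 1.077
- d = 1.2: 0.2304/0.64 = 0.36, ratio 1.166

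Simulation (N = 60, blocks of 4, 50% SMM) gives 1.019, 1.076 and 1.170, with type I error of about 4.8%, 3.6% and 2.6%. Power that would be 80% under full adjustment becomes about 79%, 76% and 70%.

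*Case B, chain status shifts both visits equally:* x = v d²(1 − ρ)²/[(1 + v d²)(1 − ρ²)], with ρ = 0.6.
- d = 0.4: 0.0256 × 0.16/(1.0256 × 0.64) = 0.006, ratio 1.003
- d = 0.8: 0.1024 × 0.16/(1.1024 × 0.64) = 0.023, ratio 1.012
- d = 1.2: 0.2304 × 0.16/(1.2304 × 0.64) = 0.047, ratio 1.023

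Simulation gives increases of about 0.2%, 0.9% and 2.1%. These are slightly lower because the added covariate uses a degree of freedom. Type I error is near 5%. At ρ = 0.9 and d = 1.2, x = 0.2304 × 0.01/(1.2304 × 0.19) = 0.010, an increase of 0.5% by formula and about 0.2% in simulation.

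*Case C, both visits are responses and the effect is group-by-time:* with two visits and complete data, the estimate is the difference between arms in mean change. A chain effect that is constant over time cancels. In a random-intercept example with a 1.2 SD chain effect, adding chain status as a main effect left the estimate (−0.2773) and its standard error (0.2288) unchanged.

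**4. On the M-protein scale.** A separate ANCOVA simulation assumed residual SD 0.99 g/dL, light-chain share 10 to 30%, and baseline M-protein near 0 in light-chain participants. For residual chain effects up to 0.6 g/dL, standard errors with and without chain status differed by under 1% and power by under 1 point. At 1.0 g/dL, omission made the standard error about 2 to 3% larger and power about 1.1 to 1.3 points lower.

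**The case against.** The strongest reply is that nothing is shown to be missing. The only strata that the document defines are the two in sections 5 and 12.4, so stratified testing most naturally means both. The sections on stratification call MGUS versus SMM disease stage, so disease subtype could be chain status or the cross-classification. This stands: a reader might infer that a factor is definitely left out, and the text does not establish that. It does establish that neither term is tied to the two factors, while the explicit covariate list has one entry besides baseline.

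A reader might also take the 17% and 70% figures of case A as the expected loss. They require chain status to cause up to 1.2 SD of differential change in six months with no baseline difference, and nothing in the document supports that. Section 3.1.1 defines light-chain-only participants by complete loss of the heavy chain. That is a lasting trait, so it points to case B. Nor does the document link chain status to haemoglobin, and each secondary model adjusts for its own baseline.

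Finally, the plan specifies a mixed model, not ANCOVA. Under case C, a main effect alone would change nothing. This also stands, and it shapes the fix.

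**Conclusion.** The point holds as a gap in specification: the stated models are not shown to include both stratification factors. If one is absent, the consequence is a modestly overstated standard error and a slightly conservative test. It causes no bias and no type I inflation, and it does not undermine the 80% and 90% power stated in 12.1.

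The likely size is small. With an assumed 20% light-chain share and ANCOVA, it is about 0 to 2% in standard error when chain status shifts both visits equally. It is 2 to 17% only under the follow-up-only shift of 0.4 to 1.2 SD at ρ = 0.6. It may be nil for a purely within-participant group-by-time contrast. The light-chain share, the correlation and the chain effect are all assumptions. The case for acting rests on clarity and on how little the change costs.

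**What to change.** In 12.2 and 12.7, replace disease subtype with: both randomisation stratification factors (disease stage, MGUS or SMM, and heavy- or light-chain status), as recorded at randomisation, as fixed effects. If baseline is also modelled as a response, add each factor's interaction with time, because main effects alone would not change the group-by-time estimate. State that this model is what stratified testing means, and that it applies to the secondary endpoints analysed under 12.7 as well.

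The cost is a change of wording and about one degree of freedom, or slightly more if the time interactions are needed. Both factors must already be known to randomise a participant, so no new data are required.

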12.3 Sample Size, Accrual Rate and Study Duration

Our estimated target accrual is 60 participants over 24 months, which requires a monthly accrual of 3-4 participants per month. Our goal for accrual into the study is 4 or more participants per month. Up to an additional 6 months of follow-up will be required on the last participant accrued to observe the participant’s response after the 6 months of taking metformin/placebo, for a total study duration of 2.5 years. Estimated accrual targets are provided below:

Accrual Targets				
Ethnic Category	Sex/Gender			
	Females		Males	Total
Hispanic or Latino	1	+	2	=
Not Hispanic or Latino	30	+	27	=
Ethnic Category: Total of all subjects	(A1)	+	(B1)	= (C1)
Racial Category				
American Indian or Alaskan Native	1	+	1	=
Asian	2	+	1	=
Black or African American	4	+	4	=
Native Hawaiian or other Pacific Islander	0	+	1	=
White	24	+	22	=
Racial Category: Total of all subjects	(A2)	+	(B2)	= (C2)

(A1 = A2)

(B1 = B2)

(C1 = C2)

12.4 Stratification Factors

Randomization will be stratified by disease stage (MGUS vs. SMM) and heavy- vs light-chain status.

12.5 Interim Monitoring Plan

Refer to section 11.2

12.6 Analysis of Primary Endpoints

Refer to section 12.2

12.7 Analysis of Secondary Endpoints

The secondary endpoint of this trial will be changes in a variety of biomarkers detailed in section 1.2. Changes in continuous variable outcomes will be evaluated from baseline to follow-up in the two groups using a repeated measures mixed-effects model that accounts for the correlation between baseline and follow-up measures and is generally robust to missing data. The baseline value of the dependent variable and disease subtype will be included as covariates in the regression models. Group-by-time interaction terms will be included as fixed-effects in the regression model. Model fit will be assessed using standard methods. All primary analyses will utilize stratified testing and intention-to-treat methods.⁷²

For changes in gene expression patterns, the precise methods are subject to change pending advancements in technology, but a general overview is provided below:

Paired-ended reads will be aligned against UCSC hg19 human annotation using Tophat 2.0.10; read counts for each gene will be determined using HTSeq 0.5.4. A subset of cells with more than 100,000 total reads across all genes will be selected for further analysis (70-80% of cells). To determine population average gene expression, the read counts observed in each cell will be normalized by the effective library size, determined by edgeR ‘calcNormFactors’ method. NMF-based consensus clustering will be used to cluster all single-cell RNA profiles. We will use coexpression networks-based gene prioritization tool GRAIL (<https://www.broadinstitute.org/mpg/grail/>) to select the most promising genes using gene expression signature as seeds. Cufflinks and Cuffdiff will be used to identify differentially expressed genes between the treatment arms.⁷³

Metabolite features will be analyzed as measures of peak areas, which are proportional to feature concentration and can be compared for any given metabolite. The metabolite variables will be standardized to a mean of 0 and standard deviation of 1.

For optional treatment extenders, this analysis is exploratory. We will assess the proportion of participants who are willing to take metformin for an additional 6 months. We will also evaluate response, duration of response, and depth of response according to modified IMWG criteria, or by mass spectrometry assessment.

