All bioinformatics and statistical analyses will be performed with guidance of the biostatistics and bioinformatics Core B. Briefly, BAM files aligned to the hg19 human genome will be produced using Illumina sequencing reads and the Picard pipeline⁴². SNVs will be determined using the MuTect2 algorithm⁴³, in single mode for targeted sequencing with additional filters for mutation call such as 1000 genome and COSMIC mutations. Indels and translocations will be determined by the algorithms IndelLocator³⁷ and dRanger, respectively. Focal as well as arm-level copy number variations will be determined based on WES and subsequent application of the GISTIC⁴⁴ algorithm. We will use MutSigCV⁴⁵ to detect candidate cancer genes using three signals of positive selection: (i) increased mutation burden as compared to a background model; (ii) clustering of mutations along the gene; and (iii) enrichment of mutations at likely functional sites. The output of MutSigCV consists of a list of the most significantly genomic events across samples. False-discovery rates (q values) ≤ 0.1 will be considered as significantly mutated. All candidate SNVs/indels/CNVs will be reviewed in the IGV⁴⁶.

9.4.6 RNA sequencing of tumor cells.

For RNA Sequencing, poly-A selection and cDNA synthesis will be performed, followed by library preparation, sequencing (76bp or 101bp paired reads), and sample identification with quality control. Details of experimental design are described in^{62,63-65}. We will perform library construction using a non-strand specific Illumina TruSeq Protocol and sequence coverage to 100M total reads. Analysis will be performed as described in the preliminary data and in previous studies⁶³⁻⁶⁵.

The DNA and or RNA library will be prepared at the [name] Lab, and then sequencing will be done at the following external lab:

Broad Institute Genomics Services
[name]
[name]

Sequencing data will then be provided back to [name] lab in the form of BAM file. The samples that are sent for analysis are exhausted during the process, and thus not able to be returned.

9.4.7 Single-cell sequencing of the tumor microenvironment.

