Single-cell RNA sequencing (RNA-seq) of the tumor microenvironment can define genotypic and phenotypic states of tumor cells and surrounding microenvironment, and that the microenvironment affected the gene expression program of tumor cells and their resistance to therapy. We will apply 10X genomics in this study to evaluate the tumor microenvironment and assess specific changes in cell type and transcriptional signature of BM niche cells that correlate with tumor progression or resistance to therapy.

9.4.8 cfDNA and circulating tumor cells (CTCs) from the peripheral blood.

cfDNA sequencing can be challenging because of the small fragment size of DNA in the peripheral blood (average of 166bp), the low yield of DNA and the usual low allelic fraction of tumor-derived DNA among the cfDNA. Therefore, we developed two different approaches to sequence cfDNA. The first approach applies WES and is performed by the Blood Biopsy Group at the Broad Institute. After high-speed centrifugation of frozen samples to eliminate residual cells from plasma, cfDNA was extracted using the Qiagen circulating nucleic acid kit. As little as 5ng of cfDNA was then subjected to library preparation using the Kapa HyperPlus kit, which enables us to prepare libraries from small DNA fragments and minimal DNA yield. CfDNA libraries were initially qualified for further sequencing using ultra-low-pass whole genome sequencing (ULP- WGS). The ULP-WGS is a low-cost approach developed by the Blood Biopsy Group to nominate samples containing sufficient tumor fraction in cfDNA samples for WES. Large numbers of cfDNA libraries were multiplexed and sequenced to an average of 0.1X genome-wide sequencing coverage.

9.4.9 Whole-exome sequencing of cfDNA and CTCs:

These studies will be performed at the Blood Biopsy Group at the Broad Institute in collaboration. As described in the preliminary data, cfDNA and CTCs will be subjected to library preparation using the Kapa HyperPlus kit and initially qualified for WES by ULP-WGS. The ULP-WGS will be used to nominate samples containing sufficient fraction of tumor-derived DNA for WES. Qualified matched samples will be hybridized to the Agilent XT v5 enrichment kit, with additional baits on MYC, IGH, IGL and IGK loci. For both cfDNA and CTCs, the coverage goal will be increased to 200x, which enables us to accurately call mutations even with low allelic fraction samples.

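### The gene-expression analysis is offered as an analysis of change, but the only between-arm test named has no baseline, visit or participant term

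*Combined protocol and SAP*

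**What the plan says.** Section 12.7 (Analysis of Secondary Endpoints) treats two kinds of outcome differently.

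- **Continuous outcomes** get a repeated-measures mixed model with group-by-time terms, and "The baseline value of the dependent variable and disease subtype will be included as covariates in the regression models".
- **Gene expression** gets a separate paragraph, which opens: "For changes in gene expression patterns, the precise methods are subject to change pending advancements in technology, but a general overview is provided below". The steps then work on cells. Low-read cells are filtered out; "To determine population average gene expression, the read counts observed in each cell will be normalized by the effective library size"; and "NMF-based consensus clustering will be used to cluster all single-cell RNA profiles". The paragraph closes with the only comparison of arms: "Cufflinks and Cuffdiff will be used to identify differentially expressed genes between the treatment arms".

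The Cuffdiff sentence does not say which libraries or visits enter, what counts as a replicate, whether baseline is used, or what error rate applies. Nothing links it to the mixed model.

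Other sections bear on this:

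- The Sample Collection Table (9.4.3) schedules blood and, where available, marrow at baseline and at the six-month visit. Section 9.4.4 (DNA and RNA sequencing of tumor cells) plans RNA sequencing at screening and on later marrows.
- Bulk tumor RNA sequencing is planned as well as single-cell work (9.4.6): "We will perform library construction using a non-strand specific Illumina TruSeq Protocol and sequence coverage to 100M total reads".
- Marrow is optional and taken only when standard care calls for it (9.4.1).
- The only q-value rule, 0.1 or less, concerns mutated genes (9.4.5).

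**The concern.** The paragraph's stated aim and its named test do not match. An analysis of change needs the two visits of one participant to be linked; a plain contrast of arms does not link them. The continuous outcomes in the same section have that link and gene expression does not, even though paired sampling is planned.

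Three things are at stake for the immune-landscape objective and, in part, the molecular-evolution objective, which rests mainly on DNA sequencing.

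1. Baseline information that the trial sets out to collect is not used, so precision is lost.
2. The participants with marrow are a self-selected and clinically selected part of the 60. Without baseline, differences in who was sampled cannot be separated from an effect of metformin.
3. Participants were randomized, not cells, but the text does not exclude counting cells as replicates. That choice largely determines whether the p-values are valid.

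**Working it through.** **The plan's own figure.** No sample size, power or error rate is given for gene expression. The only stated power is for M-protein (12.1): SD 0.99 g/dL, 60 participants, so 30 per arm. With SE = 0.99 × √(2/30) = 0.2556, the noncentrality is 0.73/0.2556 = 2.86 and 0.84/0.2556 = 3.29. A two-sided 5% t-test on 58 df then has power 80.2% and 89.8%. The stated 80% and 90% reproduce, but they do not bear on this point.

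**Precision lost without baseline.** No visit is named, so take the reading most favourable to the plan: follow-up profiles compared between arms, one per participant. Let rho be the correlation of baseline and follow-up expression. It is not in the documents and is assumed here. Relative to follow-up only (variance 1), a change score has variance 2(1 − rho) and baseline adjustment has 1 − rho².

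| rho (assumed) | follow-up only | change score | baseline-adjusted |
|---|---|---|---|
| 0.3 | 1 | 1.40 | 0.91 |
| 0.5 | 1 | 1.00 | 0.75 |
| 0.7 | 1 | 0.60 | 0.51 |
| 0.9 | 1 | 0.20 | 0.19 |

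At rho 0.5 the follow-up-only comparison needs 1/0.75 = 1.33 times as many participants as the adjusted one; at rho 0.7, 1/0.51 = 1.96 times.

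**Does leaving out baseline raise the false-positive rate?** No, if the randomized arms are intact. Simulated type I error of a follow-up-only, participant-level t-test (20,000 runs each) was 5.2% and 5.0% with 10 per arm at rho 0.5 and 0.9, and 4.9% and 5.1% with 30 per arm.

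**What if cells were the replicates?** The text does not say so; this is a conditional calculation. With m cells per participant and intraclass correlation ICC, both assumed, the design effect is DE = 1 + (m − 1) × ICC. The true level of a nominal 5% test is 2 × (1 − Φ(1.96/√DE)).

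- m = 50, ICC 0.01: DE = 1.49, level 10.8%.
- m = 100, ICC 0.01: DE = 1 + 99 × 0.01 = 1.99, level 16.5%.
- m = 100, ICC 0.05: DE = 5.95, level 42.2%.
- m = 100, ICC 0.10: DE = 10.9, level 55.3%.
- m = 1,000, ICC 0.20: DE = 200.8, level 89.0%.

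Simulation with 100 cells agrees (4,000 runs each). At ICC 0.01 the cell-level test rejected in 15.9% (10 per arm) and 17.5% (30 per arm) of null data sets. Averaging to one value per participant gave 4.9% and 5.4%. Over all the settings simulated, the participant-level test stayed between 4.5% and 5.4%.

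**The case against.** The strongest reply is that this is an overview of a correlative analysis, expressly open to revision, on samples that may never be collected. Under randomization, a follow-up contrast between arms has the same expected value as a contrast of changes, so the named test could still be valid. Much of this stands. It limits the severity and confines the loss among intact randomized arms to precision. It does not remove the point. The reason given for later revision is advancing technology, whereas the unit of inference, the use of baseline and the error rate are design choices that can be fixed now. Nor is intact randomization assured in an optional marrow subset.

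A reader might infer more, and the documents do not support it:

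- **That the plan treats cells as replicates, so false positives are inflated.** The surrounding steps are single-cell, which makes this tempting. But no unit is stated, the reference to a population average may mean aggregation, and bulk libraries could be what Cuffdiff receives.
- **That omitting baseline inflates type I error.** Between randomized arms it does not, as shown above.
- **That the filter of 100,000 reads per cell contradicts the platform.** Section 9.4.7 says only "We will apply 10X genomics in this study to evaluate the tumor microenvironment". No single-cell sequencing depth is given, so no mismatch can be shown.

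**Conclusion.** The point holds as a cheap improvement to a provisional secondary analysis, of low to moderate severity. It is more than missing detail: the one between-arm test named is not an analysis of change and makes no use of the planned baseline samples.

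The loss of precision depends on an assumed correlation; for rho from 0.3 to 0.9 the adjusted variance is 0.91 to 0.19 of the unadjusted. Possible imbalance in the marrow subset cannot be sized, because the documents do not give the number of participants with paired samples. The error inflation is conditional on cells being the replicates. In that case it runs from about 11% to 89% over an assumed 50 to 1,000 cells and ICC 0.01 to 0.20, and it vanishes with one value per participant. The primary M-protein analysis is not touched.

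**What to change.** Replace the Cuffdiff sentence in 12.7 with text that:

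1. states which libraries enter the test, single-cell, bulk or both, and from which visits;
2. makes the participant the unit, with counts summed to one profile per participant, visit and cell type, or one bulk library per participant and visit;
3. fits a count model, for example in edgeR, which the section already uses for normalization, with participant, visit and arm-by-visit terms, and takes the arm-by-visit effect as the result;
4. sets a false-discovery rate for expression in advance, since the existing 0.1 rule covers mutated genes only;
5. reports participants without paired samples descriptively or in a sensitivity analysis.

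One choice should be made knowingly. With participant as a fixed term, the arm-by-visit effect behaves like the change score in the table, which beats a follow-up-only comparison only when rho exceeds 0.5. The full 1 − rho² gain needs baseline expression as a covariate. The participant-term model is the direct test of change and protects against baseline imbalance among those with pairs.

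The cost is SAP wording, with software already named. The downsides are fewer genes called significant than under a cell-level analysis, and unpaired optional marrow samples that add little to the main test.
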